9.3.6. Pharmacokinetic Analyses

GLPG3970 plasma concentrations will be listed and predose concentrations (C_{trough}) will be summarized descriptively.

All observed GLPG3970 plasma concentrations will be analyzed using a population PK approach to characterize the PK profile of GLPG3970 and determine the PK parameters (e.g. clearance and volume of distribution) and their associated variability. The influence of covariates may be investigated.

[REDACTED]

[REDACTED]

9.3.7. [REDACTED]

[REDACTED]

9.3.8. Additional Statistical Considerations

Not applicable.

10. DATA MONITORING

10.1. Data Safety Monitoring Committee

An Internal Data Safety Monitoring Committee independent from the study will review unblinded data during the course of the study. This Committee may involve external medical experts (such as an expert in the field of UC and an infectious diseases expert) to support data interpretation. The Committee will review unblinded safety data and assess any potential safety issues arising during the conduct of the clinical study, including (but not limited to) any potential issues in the context of the SARS-CoV-2 pandemic. The process is described in a separate 'Internal Safety Monitoring Committee Charter'.

11. SAFETY REPORTING

11.1. Definitions of Adverse Events, Serious Adverse Events, and Special Situations

11.1.1. Adverse Events

An AE is any untoward medical occurrence, new or worsening of any preexisting condition, in a clinical study subject administered a medicinal product and which does not necessarily have to have a causal relationship with this treatment.

An AE can therefore be any unfavorable and unintended sign (e.g. an abnormal laboratory finding), symptom, or disease temporally associated with the use of a medicinal product, whether or not considered related. AEs may also include pre- or post-treatment complications that occur as a result of CSP-specified procedures, worsening of the targeted disease, overdose, drug abuse/misuse reports, or occupational exposure. Preexisting conditions that increase in severity or change in nature during or as a consequence of participation in the clinical study will also be considered AEs.

11.1.2. Serious Adverse Events

An SAE is defined as an AE that:

- Results in death.
- Is life-threatening (Note: The term 'life-threatening' in the definition of 'serious' refers to an event in which the subject was at risk of death at the time of the event; it does not refer to an event that hypothetically might have caused death if it were more severe.).
- Requires in-patient hospitalization or prolongation of existing hospitalization.
- Results in persistent or significant disability/incapacity.
- Is a congenital anomaly / birth defect.
- Is medically significant (medical and scientific judgment should be exercised in deciding whether other situations should be considered serious such as important medical events that might not be immediately life-threatening or result in death or hospitalization but might

jeopardize the subject or might require intervention to prevent one of the other outcomes listed in the definition above).

11.1.3. Unlisted (Unexpected) Adverse Events/ Reference Safety Information

An AE is considered unlisted if the nature or intensity is not consistent with the applicable product reference safety information. For an IP, the expectedness of an AE will be determined by whether or not it is listed in the reference safety information part of the IB.

11.1.4. Adverse Events of Special Interest

Not applicable.

11.1.5. Clinical Laboratory Abnormalities and Other Abnormal Assessments as Adverse Events or Serious Adverse Events

Laboratory abnormalities without clinical significance based on the investigator's judgment are not considered AEs or SAEs. However, laboratory abnormalities (e.g. clinical chemistry, hematology, and urinalysis) or other abnormal (clinical study-specific) assessments (e.g. ECG, radiography, vital signs) that require medical or surgical intervention, are associated with signs and/or symptoms, and/or lead to IP interruption, modification or discontinuation must be recorded as an AE or SAE if they meet the definition as described in Sections 11.1.1 and 11.1.2, respectively. If the laboratory abnormality is part of a syndrome, the syndrome or diagnosis is to be reported (e.g. anemia instead of decreased hemoglobin).

The following liver enzyme elevations should be reported as SAEs:

- AST or ALT \geq 8xULN.
- AST or ALT \geq 3xULN with signs of liver damage (total bilirubin $>$ 2xULN OR international normalized ratio $>$ 1.5, and/or with the appearance of fatigue, nausea, vomiting, right upper quadrant pain or tenderness, fever, rash and/or eosinophilia [$>$ 5%]).

11.1.6. Special Situations

Special situations are situations that have a possible impact on the safe use of the IP. These situations might be or might not be associated with AEs.

- Pregnancy.
- Overdose with IP.
An overdose of IP is defined as the administration of a quantity of the IP given per administration or cumulatively, which is above the recommended dose in the protocol.
- Medication error with IP.
A medication error with IP is defined as an unintended failure in the drug treatment process that leads to, or has the potential to lead to, harm to the subject.
- Product complaint or quality defect of IP.

Product complaint or quality defect of IP is defined as complaints or defects of the IP arising from potential deviations in the manufacture, packaging, or distribution of the IP.

- Drug interaction or food interaction with IP.

A drug interaction with IP is defined as a situation in which there is evidence or a suspicion that the IP interacts with another drug when both are administered together.

A food interaction with IP is defined as a situation in which there is evidence or a suspicion that the IP interacts with a food when taken together.

- Occupational exposure to IP.

Occupational exposure to IP is defined as an exposure to the IP as a result of one's professional or non-professional occupation.

11.2. Assessment of Adverse Events and Serious Adverse Events

The investigator is responsible for assessing AEs and SAEs for causality and severity. This is the basis for the sponsor's final review and confirmation of accuracy and completeness of event information and causality assessments.

11.2.1. Action Taken Regarding Investigational Product

The action taken must be described by choosing from:

- Dose not changed: In case no action is taken regarding the IP.
- IP permanently discontinued: In case a subject is permanently discontinued from treatment or withdrawn from the study by the investigator (who may consult the sponsor's medical monitor).
- IP temporarily discontinued: In case the IP is temporarily discontinued by the investigator (who may consult the sponsor's medical monitor).
- Not applicable: Other situations (e.g. in case an AE started after the last IP administration).

11.2.2. Assessment of Causality

The investigator is responsible for assessing the causal relationship to IP(s) administration or study procedures (e.g. invasive procedures such as venipuncture) based on her/his clinical judgment. The following decision choice will be used by the investigator to describe the causality assessment between the reported event or laboratory test abnormality and the IP.

- **Unrelated:**

Time relationship to IP intake is improbable. Related to other etiologies such as concomitant medications or subject's clinical state.

- **Unlikely:**

Time relationship to IP intake is improbable (but not impossible). Concomitant disease or other drugs provide plausible explanations.

- **Possible:**
Time relationship to IP intake is reasonable. Event or laboratory test abnormality could also be explained by disease or other drugs. Information on IP withdrawal may be lacking or unclear.
- **Probable:**
Time relationship to IP intake is reasonable. Unlikely to be attributed to concurrent disease or other drugs. Response to withdrawal is clinically reasonable and rechallenge not required.
- **Certain:**
Time relationship to IP intake is plausible. Cannot be explained by concomitant disease or other drugs. Response to withdrawal is plausible (pharmacologically, pathologically). Event definitive pharmacologically or phenomenologically (i.e. an objective and specific medical disorder or a recognized pharmacological phenomenon). Rechallenge satisfactory, if ethical and necessary.

It should be emphasized that ineffective treatment (worsening of the disease) should not be considered as causally related in the context of AE reporting.

11.2.3. Assessment of Severity

The severity of AEs should be graded using the CTCAE version current at the time of assessment. If a CTCAE criterion does not exist, the investigator should use the grade or adjectives: Grade 1 (mild), Grade 2 (moderate), Grade 3 (severe), Grade 4 (life-threatening), or Grade 5 (fatal) to describe the maximum intensity of the AE. For purposes of consistency with the CTCAE, these intensity grades are defined in [Table 1](#).

Table 1: Grading of AE Severity

| Grade | Adjective | Description |
|---------|------------------|---|
| Grade 1 | Mild | Asymptomatic or mild symptoms; clinical or diagnostic observations only; intervention not indicated |
| Grade 2 | Moderate | Local or noninvasive intervention indicated; limiting age-appropriate instrumental ADL* |
| Grade 3 | Severe | Severe or medically significant but not immediately life-threatening; hospitalization or prolongation of hospitalization indicated; disabling; limiting self-care ADL** |
| Grade 4 | Life-threatening | Urgent intervention indicated |
| Grade 5 | Death | Death-related AE |

* Instrumental Activities of Daily Living (ADL) refer to preparing meals, shopping for groceries or clothes, using the telephone, managing money, etc.

** Self-care ADL refer to bathing, dressing and undressing, feeding self, using the toilet, taking medications, and not bedridden.

For AEs associated with laboratory abnormalities, the event should be graded on the basis of the clinical severity in the context of the underlying conditions; this may or may not be in agreement with the grading of the laboratory abnormality. This is upon the investigator's assessment.

If there is a change in intensity (worsening or improvement) of an AE, it must be recorded.

11.2.4. Outcome

Each AE must be rated by choosing among:

- Recovered/resolved;
- Recovered/resolved with sequelae;
- Recovering/resolving;
- Not recovered/not resolved;
- Fatal;
- Unknown.

11.3. Instructions for Reporting Adverse Events, Serious Adverse Events, Pregnancies, and Other Special Situations

11.3.1. Adverse Events

The AE reporting period for safety surveillance begins when the subject signs the ICF and ends at the subject's last follow-up visit (the last follow-up visit after the last dose of IP). In this period, all new AEs, regardless of cause or relationship, derived by spontaneous, unsolicited reports of subjects, by observation and by routine open questioning (such as "How do you feel?") need to be recorded in the source and in the CRF.

In case an AE is ongoing at the time of the last follow-up visit, the investigator needs to follow-up on the subject until AE resolution or reasonable stabilization and to document in the subject's source documentation. No related updates or additional data on the AE should be reported in the CRF.

If a subject is documented as lost-to-follow-up, ongoing/unknown outcome AEs will not be followed-up.

If the AE meets the criteria for seriousness, the SAE form must be completed and sent to the sponsor within 24 hours (see Section [11.3.2](#)).

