9.3.5.2. Adverse Events

Clinical and laboratory AEs will be coded using the latest version of the Medical Dictionary for Regulatory Activities. System Organ Class, High-Level Group Term, High-Level Term, Preferred Term, and Lower-Level Term will be attached to the clinical database.

The following AEs will be considered as TEAEs:

Any AE with an onset date on or after the IP start date and no later than 14 days after last dose of IP, or any worsening of any AE on or after the IP start date. Investigators are not obliged to actively seek SAEs after the CSP defined follow-up period. However, if the investigator is informed about SEA that occurs at any time after the subjects post-treatment follow-up visit and the event is deemed relevant to the use of IP, they should promptly document and report the event to the sponsor by using the SAE form.

Summaries (number and percentage of subjects) of TEAEs per subject by System Organ Class and Preferred Term will be provided by treatment group. TEAEs will also be summarized by causal relationship to the IP and severity. In addition, TEAEs leading to ED of the IP will be summarized and listed. Also, all SAEs, including the non-treatment-emergent SAEs, will be listed.

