11.3.2. Serious Adverse Events

Subjects experiencing an SAE or an emergency situation will be examined by a physician as soon as possible. The subject will remain under observation as long as medically indicated.

Appropriate laboratory tests will be performed until all parameters return to normal or are otherwise explained or stable.

All SAEs, whether or not deemed IP-related, must be recorded on the SAE form and in the CRF. The investigator must report each SAE immediately, and under no circumstances should this exceed 24 hours following the knowledge of the SAE, as is indicated on page 2 under "Emergency Contact Information".

The SAE form should at least contain identifiers of the subject and the reporter, SAE term and statement of relatedness to the IP, and at a later stage if not yet available within 24 hours, the form needs to be completed with a clearly written narrative describing signs, symptoms, and treatment of the event, diagnostic procedures, as well as any relevant laboratory data and any sequelae.

Follow-up and outcomes should be reported and documented in the source documents for all subjects that experience an SAE. It is important that the information provided on the SAE form matches the information recorded on the CRF for the same event.

Copies of additional laboratory tests, consultation reports, post-mortem reports, hospital case reports, autopsy reports, and other documents should be sent when requested and available. Only subject identifiers (subject number) should appear on the copies, and all names and initials should be blackened and rendered illegible. Follow-up reports relative to the subject's subsequent course must be submitted until the event has subsided or, in case of permanent impairment, until the condition stabilizes.

Any SAEs that occur after the post-treatment follow-up visit but within 30 days of the last dose of IP(s), regardless of causality, should also be reported (Emergency Contact Information on page 2) but not entered in the CRF. Investigators are not obligated to actively seek SAEs after the CSP-defined follow-up period. However, if the investigator is informed about an SAE that occurs at any time after the subjects' post-treatment follow-up visit and the event is deemed relevant to the use of IP(s), he/she should promptly document and report the event to the sponsor by using the SAE form.

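### Protocol 11.3.1 bars CRF updates for any adverse event open at the last follow-up visit, with no exception for SAEs, which conflicts with the SAE rules in 11.3.2

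*Protocol*

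**What the plan says.** Protocol 11.3.1 ends the AE reporting period at the last follow-up visit, planned 14±3 days after the last dose. An AE still ongoing then is followed to resolution or reasonable stabilisation, with documentation in the source. On the CRF the rule is: "No related updates or additional data on the AE should be reported in the CRF". The same section says that a serious event needs an SAE form within 24 hours and points to 11.3.2. It does not lift the CRF bar for such events.

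Protocol 11.3.2 requires every SAE on both the SAE form and the CRF. Follow-up reports on the subject's "subsequent course must be submitted until the event has subsided" or, for permanent impairment, until the condition stabilises. It adds: "It is important that the information provided on the SAE form matches the information recorded on the CRF for the same event". SAEs that occur after the follow-up visit but within 30 days of the last dose are reported "but not entered in the CRF".

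Three other protocol rules bear on the point. Section 11.2.3 says: "If there is a change in intensity (worsening or improvement) of an AE, it must be recorded". It does not say where. Section 11.2.4 offers "Not recovered/not resolved" among the outcome categories. Section 9.3.5.2 promises: "Also, all SAEs, including the non-treatment-emergent SAEs, will be listed".

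SAP 6.3.1 says that AEs and changes in their attributes are in the database. SAP 6.3.1.8 tabulates subjects with serious treatment-emergent AEs (TEAEs), TEAEs leading to death, and TEAEs by worst intensity.

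**The concern.** An SAE can be open at the last follow-up visit and change afterwards. Section 11.3.2 then makes the SAE form change and requires it to agree with the CRF, while 11.3.1 says that the CRF entry may not be touched. Read literally, a site cannot follow both.

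What is at stake is the reported status of an event already counted as a TEAE. A death that follows the visit could stand in the CRF as "Not recovered/not resolved", although site and sponsor hold the true outcome on the SAE form. Severity is part of the named secondary endpoint (Protocol 4.2), and this is the first study of GLPG3970 in patients with ulcerative colitis (Protocol 5.5), so the death and worst-grade rows should be right.

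**Working it through.** **Which rule applies to which event**

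| Event at the last follow-up visit | Protocol 11.3.1 | Protocol 11.3.2 | Result if 11.3.1 is followed |
|---|---|---|---|
| SAE, already in the CRF, still open | No CRF update | Reports continue; SAE form must match the CRF | Conflict. Outcome and grade go stale. The serious flag is already correct. |
| Non-serious AE, open, later becomes serious | No CRF update | SAE form needed; the exclusion from the CRF can be read to cover it | Gap, not contradiction. The serious flag can be missing. |
| Non-serious AE, open, later worsens but stays non-serious | No CRF update | Does not apply | Later grade is not collected. This is a cut-off choice. |

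In the first row, the TEAE-leading-to-death row and the worst-grade row can be wrong. In the second, the serious-TEAE row and possibly the SAE listing of 9.3.5.2 can be incomplete, but only if tables and listings use CRF data alone.

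The second row can arise by rule. Protocol 11.1.5 states: "The following liver enzyme elevations should be reported as SAEs". The list covers AST or ALT at 8xULN or more, and 3xULN or more with signs of liver damage. An elevation from 3 to below 8xULN without such signs, recorded as a non-serious AE and open at the visit, becomes an SAE if it later meets either condition.

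**Size per subject**

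Planned arms are 20 and 10 (Protocol 9.1). One subject not already in the row moves it by 1/20 = 5 percentage points on GLPG3970 or 1/10 = 10 points on placebo.

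**Expected frequency**

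The documents give no AE counts, durations or rates of late serious turn. The following are assumptions:
- N = 30 to 60 TEAEs in the trial.
- Mean duration m = 7 to 28 days, exponential, with onsets uniform over T = 43 + 14 = 57 days.
- w = 0.5% to 2% of AEs open at the visit later turn serious or fatal.

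Share open at the visit = (m/T)(1 − exp(−T/m)):
- m = 7: 0.123
- m = 14: 0.241
- m = 28: 0.427

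Expected events = N × share × w:
- Low: 30 × 0.123 × 0.005 = 0.018
- Middle: 30 × 0.241 × 0.01 = 0.072, to 60 × 0.241 × 0.01 = 0.145
- High: 60 × 0.427 × 0.02 = 0.51

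The high case combines all three upper values. Every scenario is below one event.

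**The case against.** The strongest defence is that 11.3.1 is the general rule and 11.3.2 the specific one. Section 11.3.1 refers serious events to 11.3.2, so a site could treat 11.3.2 as governing and keep updating SAEs in the CRF. That reading is reasonable, but the text does not state it. Section 11.3.2 also sends follow-up and outcomes to the source documents, which supports the opposite reading. The ambiguity remains.

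A second defence is that the cut-off is deliberate. AE reporting ends at the visit, SAEs occurring later are kept out of the CRF, and an unresolved outcome is the true status at that date. This stands for non-serious AEs. It does not explain why the SAE form must match a CRF entry that may not change.

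A third is that the documents' silence on merging SAE-form data proves little. Protocol 12.7.1 refers to a Data Management Plan, and SAP section 1 to a separate document on derivations. Neither is available here. This stands, and it makes the effect on the tables conditional.

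Some stronger readings are tempting but not supported:
- **The conflict removes serious events from the serious-TEAE row.** It does not: an SAE already in the CRF is already flagged as serious. A missing serious count can arise only from the late-turn gap.
- **Section 11.3.1 contradicts SAP 6.3.1 for every AE.** The SAP sentence describes database content and can be read as limited to the AE reporting period. At most this is a tension in wording. Protocol 11.2.3 can be met by recording in the source.
- **The part of the TEAE definition on worsening, which has no end date, requires later collection.** SAP 4.3.2 ends the last analysis period at last contact, and the definition can be applied within that limit.

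**Conclusion.** The point holds for SAEs already in the CRF and open at the last follow-up visit. As written, 11.3.1 freezes their outcome and grade while 11.3.2 requires the SAE form, which must keep changing, to agree with the CRF. For an AE that starts before the visit and first becomes serious afterwards, there is a conditional gap.

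The severity is minor. One subject moves a row by 5 or 10 points, and the expected number of events is 0.02 to 0.5 under assumptions that have no source in the documents. A reader might infer a weakness in safety surveillance, but the SAE form still goes to the sponsor within 24 hours. The SAP safety estimand, the percentage of subjects with TEAEs, is also unaffected, because such an event is already counted. The effect on the tables rests on sites following 11.3.1 literally and on no merge of SAE-form data before the tables are made.

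**What to change.** In Protocol 11.3.1, add that the CRF bar does not apply to an AE with onset on or before the last follow-up visit that is, or becomes, serious or fatal. Its seriousness, grade and outcome are updated in the CRF and reconciled with the SAE form until database lock.

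In Protocol 11.3.2, limit the exclusion from the CRF to SAEs with new onset after the visit.

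SAP 6.3.1.3 allocates AEs to analysis periods by their start date, so these events stay in the treatment period. Neither the analysis period in SAP 4.3.2 nor the worsening part of the TEAE definition needs to change. The bar can remain for all other non-serious AEs.

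The cost is a sentence or two in each of the two protocol sections and a few CRF entries from data already on the SAE form. No visit or active search is added. The downside is that some late outcomes may reflect the underlying disease or the post-study ulcerative colitis medication allowed in Protocol 12.6.1, and the tables would include them.

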11.3.2. Serious Adverse Events

Subjects experiencing an SAE or an emergency situation will be examined by a physician as soon as possible. The subject will remain under observation as long as medically indicated.

Appropriate laboratory tests will be performed until all parameters return to normal or are otherwise explained or stable.

All SAEs, whether or not deemed IP-related, must be recorded on the SAE form and in the CRF. The investigator must report each SAE immediately, and under no circumstances should this exceed 24 hours following the knowledge of the SAE, as is indicated on page 2 under "Emergency Contact Information".

The SAE form should at least contain identifiers of the subject and the reporter, SAE term and statement of relatedness to the IP, and at a later stage if not yet available within 24 hours, the form needs to be completed with a clearly written narrative describing signs, symptoms, and treatment of the event, diagnostic procedures, as well as any relevant laboratory data and any sequelae.

Follow-up and outcomes should be reported and documented in the source documents for all subjects that experience an SAE. It is important that the information provided on the SAE form matches the information recorded on the CRF for the same event.

Copies of additional laboratory tests, consultation reports, post-mortem reports, hospital case reports, autopsy reports, and other documents should be sent when requested and available. Only subject identifiers (subject number) should appear on the copies, and all names and initials should be blackened and rendered illegible. Follow-up reports relative to the subject's subsequent course must be submitted until the event has subsided or, in case of permanent impairment, until the condition stabilizes.

Any SAEs that occur after the post-treatment follow-up visit but within 30 days of the last dose of IP(s), regardless of causality, should also be reported (Emergency Contact Information on page 2) but not entered in the CRF. Investigators are not obligated to actively seek SAEs after the CSP-defined follow-up period. However, if the investigator is informed about an SAE that occurs at any time after the subjects' post-treatment follow-up visit and the event is deemed relevant to the use of IP(s), he/she should promptly document and report the event to the sponsor by using the SAE form.

